8.1. Adverse events

In addition to the pre-specified safety outcomes, participants will be asked about any adverse events occurring or worsening since the time of infusion. An *adverse event* will be defined as

Study Name: The Fragility Fracture Trial
Version No: 2
Date: 2020-10-04
EudraCT No: 2019-004766-17

is done by the International Conference on Harmonisation of Technical Requirements for Registration of Pharmaceuticals for Human Use (ICH):⁵⁰

Any untoward medical occurrence in a patient or clinical investigation subject administered a pharmaceutical product and which does not necessarily have to have a causal relationship with this treatment.

The principal investigators or research nurses will interview participants about adverse events at each study contact. The questions will be open-ended, instead of directed at particular types of events. Participants will also have the possibility of reporting adverse events between the scheduled contacts. Participants who withdraw will be asked if they wish to answer questions about adverse events before they formally withdraw.

The following information will be collected about adverse events:

1. Type of event (diagnosis, symptom(s), or abnormal laboratory value)
2. Duration (start date and, if applicable, stop date)
3. Causality (suspected/not suspected to be related to zoledronic acid or placebo)
4. Seriousness (serious/non-serious)
5. Expectedness (expected/unexpected) (applicable only if the event is suspected to be causally related to zoledronic acid or placebo)
6. Actions taken
7. Outcome

The severity of the adverse event (e.g., mild, moderate, or severe) will not be recorded because this information is not legally required and is unlikely to be analyzed.

Participants who have been affected by an AE will be followed-up according to the clinical practice of the study center until the adverse event is resolved or stable. Participants with AEs that are suspected to be related to the investigational product will be followed-up until they have recovered or are well taken care of and on the way to good recovery.

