Given the high incidence of non-hip, non-vertebral fractures, the high risk of recurrent fractures, and the seriousness of hip and vertebral fractures, which occur later in life than other types of fractures, it would be of high interest to study whether bone-protective therapy is effective in older adults who are selected solely for having a history of non-hip, non-

Study Name: The Fragility Fracture Trial
Version No: 2
Date: 2020-10-04
EudraCT No: 2019-004766-17

vertebral fracture, without prior assessment of bone mineral density. Increased treatment of this patient group is feasible because only around 10% of Swedish fracture patients aged 50 or older receive treatment.^{15,16}

Zoledronic acid is a well-known and well-studied bone-protective agent, which was approved in the European Union in 2005.¹⁷ Zoledronic acid reduces bone resorption and belongs to the bisphosphonate class.¹⁸ In three large clinical trials, zoledronic acid was shown to reduce the risk of clinical fracture in women with osteoporosis, in women with osteopenia, and in men and women with a hip fracture.^{19–21} Although a fourth trial conducted in men with osteoporosis did not show a significant effect of zoledronic acid on clinical fractures, this trial was smaller and it did show a significant effect on radiologically detected vertebral fractures.²²

The most common adverse effects of zoledronic acid are transient post-infusion symptoms (pyrexia, myalgia, headache, arthralgia, and influenza-like symptoms), which occur in about one third of patients in the first 3 days following an initial infusion.¹⁹ These symptoms are less common after subsequent infusions.¹⁹ Zoledronic acid and other bisphosphonates have been associated with two rare but serious adverse effects: atypical femoral fractures and osteonecrosis of the jaw.^{23,24} However, osteonecrosis of the jaw does not primarily occur in osteoporosis patients but in cancer patients, who receive much higher doses of zoledronic acid to reduce the adverse skeletal effects of cancer (e.g., bone metastases).²³ In osteoporosis patients, the incidence of osteonecrosis of the jaw is estimated to be 1 in 100,000 to 1 in 10,000.²³ Atypical femoral fractures are also rare, and they are typically reported after long treatment periods of 7 or more years.^{25,26} It should also be noted that no increased risk of these adverse events was reported in the four largest trials of zoledronic acid that have been conducted to date.^{20–22,26}

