5.2. Exclusion criteria

Patients will be excluded from the trial if they meet any one of the following criteria:

1. History of hip fracture or vertebral compression fracture
2. Undergone bone density scanning since the fragility fracture
3. Severe renal impairment (estimated glomerular filtration rate of <35 ml per minute per 1.73 m² of body surface area)
4. Remaining life expectancy of <1 year, according the investigator's judgement
5. Hypocalcemia (serum calcium <2.2 mmol/L)
6. Sarcoidosis (contraindication for vitamin D)

Study Name: The Fragility Fracture Trial
Version No: 2
Date: 2020-10-04
EudraCT No: 2019-004766-17

7. Previous use of bone-protective drug (e.g., bisphosphonate, teriparatide, denosumab, raloxifene, or strontium ranelate; calcium and vitamin D are acceptable)
8. Use of systemic glucocorticoids at a dose of ≥ 5 mg (prednisolone or equivalent) for ≥ 3 months in the past year
9. Other medication or medical condition for which bone-protective therapy is indicated (e.g., bone metastases or use of aromatase inhibitor; osteoporosis is permitted)

Patients with a hip or vertebral fracture will be excluded because these patients should receive bone-protective therapy according to current Swedish national guidelines.⁴⁰ Patients who have undergone bone density scanning will be excluded because the inclusion of these patients could skew the study population toward low-risk patients who do not qualify for treatment according to current guidelines, which would reduce the statistical power of the trial.

6. Investigational Products

Zoledronic acid (5 mg) or placebo (normal saline) will be given as a 15-minute intravenous infusion at baseline and at 2 years. The volume of fluid will be 100 ml (5 ml of zoledronic acid or placebo + 95 ml of mannitol, sodium citrate, and water for injections). A flush of 10 ml of normal saline will be given before and after administration, resulting in a total of 120 ml of intravenously infused fluid. All patients will receive advice about nutrition and exercise to prevent new fractures.

Zoledronic acid can cause post-infusion symptoms (pyrexia, myalgia, headache, arthralgia, or influenza-like symptoms) within the first 3 days.¹⁹ Patients will be informed that these symptoms may be uncomfortable but that they are not dangerous and can be eased with paracetamol if needed.

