7.4. Safety outcomes

Based on previous trials of zoledronic acid and the Summary of Product Characteristics of Aclasta,^{17,19-21} the occurrence or worsening of the following pre-specified safety outcomes will be assessed:

1. Post-infusion symptoms
 - a. Influenza-like symptoms
 - b. Pyrexia
 - c. Myalgia
 - d. Headache
 - e. Arthralgia
2. Osteonecrosis of the jaw
3. Osteonecrosis (avascular necrosis) not of the jaw
4. Atypical femur fracture
5. Any atrial fibrillation
6. Serious atrial fibrillation
7. Re-operation of fracture
8. Delayed fracture healing
9. Renal failure
10. Hypocalcemia
11. Ocular event

In the 10-year follow-up, ICD-10-SE codes will be used to trace occurrences of atrial fibrillation (I48), renal failure (N17-N19), hypocalcemia (E835) femur shaft fractures (S722-S724), ocular events (H10-H22), osteonecrosis not of the jaw (M87), and inflammatory conditions of the jaw (K10.2) in Swedish National Patient Register.

8. Safety

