Follow-up interviews will be conducted by telephone every six months for 48 months for assessment of outcomes, adverse events, use of the prescribed vitamin D, and use of non-investigational bone-protective therapy. At every second interview, participants will be asked to complete the EQ-5D-5L online. The telephone interviews may be conducted with a next of kin if the participant is unable to respond and if the participant has consented to this. Halfway through the trial, at 24 months, participants will visit their study center for an in-person interview, outcome assessment, and a second infusion of zoledronic acid or placebo. Participants who have not taken their monthly vitamin D, or who have not taken a sufficient amount in the investigator's opinion, will receive a second loading dose of vitamin D one week before the second infusion. The final study contact, at 48 months, will be a telephone interview instead of an in-person visit to reduce the burden on investigators. Participants will be followed through registers for ten years after randomization, so that the long-term effects of zoledronic acid can be evaluated. Participants will be given the choice to opt out of registry follow-up.

Study Name: The Fragility Fracture Trial
Version No: 2
Date: 2020-10-04
EudraCT No: 2019-004766-17

Investigators must do their best to ensure that study contacts occur in the designated time windows by scheduling study contacts in good time. To reduce the burden on investigators, telephone interviews will be conducted centrally from the sponsor/coordinating investigator's center. Each visit is anticipated to take 1 hour and each telephone interview 30 minutes.

Study Name: The Fragility Fracture Trial
Version No: 2
Date: 2020-10-04
EudraCT No: 2019-004766-17

Table 1. Participant Timeline

Timing/procedure	Event										
	Scr	Rand	Tel 1	Tel 2	Tel 3	Vis 1	Vis 2	Tel 4	Tel 5	Tel 6	Tel 7
Time point	-7 d	0	6 m	12 m	18 m	23 m + 3 w	24 m	30 m	36 m	42 m	48 m
Time window	-4 to -1 w	0	±4 w	±4 w	±4 w	±4 w	±4 w	±4 w	±4 w	±4 w	±4 w
Informed consent	X										
Eligibility	X	X*				X**	X*				
Participant ID code	X										
Health questionnaire	X										
Body weight	X										
Blood samples	X					X					
Accelerometer	X										
Vitamin D loading dose	X					X [†]					
Vitamin D prescription	X		X	X	X	X		X	X	X	
Infusion		X					X				
Oral vitamin D use			X	X	X	X		X	X	X	X
Bone-protective drug use			X	X	X	X		X	X	X	X
Adverse event assessment			X	X	X	X		X	X	X	X

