The occurrence of falls will be analyzed as the number and percent of participants reporting at least one fall. Falls will not be analyzed as a time-to-event outcome because participants may not remember exactly when they fell. The zoledronic acid and placebo groups will be compared using relative risks, with 95% confidence intervals estimated based on the normal approximation. Participants with incomplete follow-up and who did not report a fall during follow-up will be assumed not to have fallen.

Change-from-baseline outcomes will be analyzed using analysis of covariance. The response variable will be post-intervention value and the explanatory variables will be baseline value and treatment group. For the EQ-5D-5L exploratory outcomes, which will be measured every 12 months of follow-up, an analysis of covariance will be run with each follow-up value as the post-intervention value. To prevent the problem of multiple testing, the stepwise approach to testing described in Section 13.8 will be used. The assumptions of linearity, constant variance, and normality will be checked using residual plots and normal quantile-quantile plots. Clear violations of these assumptions will be dealt with by transformations of the response variable or its baseline value. Clear violations of the assumption of constant variance may instead be dealt with using the method of weighted least squares. Outliers will not be removed. Participants with missing follow-up data on change-from-baseline variables will be excluded.

The hypothesis tests of efficacy will not be adjusted for multiple testing to avoid a large reduction in the power of the trial.

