13.7. Safety analysis

All participants who receive at least one infusion will be included in a safety analysis. The occurrence of adverse events by the end of follow-up will be analyzed as the number of events and the number and percent of participants reporting at least one event. These data will

Study Name: The Fragility Fracture Trial
Version No: 2
Date: 2020-10-04
EudraCT No: 2019-004766-17

be presented by study group, seriousness, and causality (suspected/not suspected relation to study medication). The study groups will be compared using Fisher's exact test. For post-infusion symptoms occurring ≤ 3 days after infusion, data will be presented for both infusions in total and for events reported to have occurred ≤ 3 days after each infusion. In addition to specific adverse events, the composite safety outcomes of any adverse event, any serious adverse event, any serious adverse drug reaction, any unexpected adverse drug reaction, and any suspected unexpected serious adverse reaction will be reported. Laboratory values of serum calcium (low, <2.2 mmol/l; normal, 2.2-2.6; high, >2.6)⁶² will be analyzed in a shift table from before the first to before the second infusion. The number and percent with severe renal impairment (estimated glomerular filtration rate <35 ml/min/1.73m²) at Follow-Up Visit 1 will be presented. The mean and standard deviation change in estimated glomerular filtration rate from before the first to before the second infusion will be presented and compared between the groups using an independent-samples *t* test (Satterthwaite approximation of degrees of freedom).

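### Post-infusion symptoms are tabulated by onset within 3 days of each infusion, but the first scheduled question that could capture them comes about 6 months later

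*Protocol*

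**What the plan says.** **The outcome and its analysis.** Section 6 describes the study treatment as a "15-minute intravenous infusion at baseline and at 2 years"; Table 1 (Section 9) places the infusions at the randomization visit and at Vis 2. Section 7.4 states that "the occurrence or worsening of the following pre-specified safety outcomes will be assessed", and post-infusion symptoms come first on the list, with five named components. Section 2 calls them transient and the drug's most common adverse effects, "which occur in about one third of patients in the first 3 days following an initial infusion". Section 13.7 compares adverse events between groups by Fisher's exact test. For post-infusion symptoms within 3 days it adds that "data will be presented for both infusions in total and for events reported to have occurred" in that window after each infusion.

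**The collection.** Section 9 states: "Follow-up interviews will be conducted by telephone every six months for 48 months for assessment of outcomes, adverse events". In Table 1 the row "Adverse event assessment" is marked at Tel 1 to Tel 3, Vis 1 and Tel 4 to Tel 7. It is blank at the randomization visit and at Vis 2. The pre-specified safety outcomes have no row of their own.

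Section 8.1 says of the adverse event interview: "The questions will be open-ended, instead of directed at particular types of events". It collects a start date and, where applicable, a stop date, and it allows participants to report between contacts. It presents these questions as additional to the pre-specified safety outcomes, without saying how those outcomes are elicited.

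**The concern.** The analysis needs to know whether a short-lived symptom occurred and whether it began within 3 days of an infusion. The collection schedule supplies that about half a year later, unless the participant contacts the center unprompted. Mild reactions are the ones most easily forgotten or thought not worth mentioning, and Section 6 has participants told beforehand that these symptoms are not dangerous. Section 8.1 also decides not to record severity, so the data could not show whether the reactions reported are mainly the worse ones.

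At stake is the tolerability description of a two-yearly schedule: the absolute frequency, the risk difference against placebo and the figures for each infusion. Section 17 uses the frequency of these symptoms in its own risk-benefit argument. An analysis plan cannot restore information that was not collected near the infusion, so this belongs in the protocol.

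**Working it through.** The protocol states no figure for this point, so there is none to reproduce. The check has two parts.

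**1. Delay from infusion to the first scheduled question**

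Inputs from Table 1: infusions at 0 and 24 months; next adverse event contacts at 6 months (Tel 1) and 30 months (Tel 4); window ±4 weeks (28 days) at Vis 2, Tel 1 and Tel 4. Vis 1 comes before infusion 2 and so cannot cover it.

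- Nominal delay after either infusion: 6 × 365.25/12 = 182.6 days.
- Infusion 1 to Tel 1: 182.6 ± 28 = 155 to 211 days.
- Infusion 2 to Tel 4, both windows used in full: 182.6 ± 56 = 127 to 239 days.

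The classification window is 3 days.

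**2. What incomplete reporting would do**

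Inputs from the protocol: 2900 participants randomized 1:1, so 1450 per arm; symptoms in about one third after the first infusion; two-sided 5% level.

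Assumptions, because the protocol gives no figure: the share *s* of true cases still reported about 6 months later, equal in both arms; and a placebo rate *p*, shown at 10% and varied from 5% to 15%.

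True cases on zoledronic acid: 1450/3 = 483. Observed rate = *s*/3; cases missed = 483 × (1 − *s*); observed risk difference = *s* × (1/3 − *p*).

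| Share reported | Observed rate, zoledronic acid | Cases missed | Risk difference at *p* = 10% |
|---|---|---|---|
| 100% | 33.3% | 0 | 23.3 points |
| 75% | 25.0% | 121 | 17.5 points |
| 50% | 16.7% | 242 | 11.7 points |
| 25% | 8.3% | 362 | 5.8 points |

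Power for the between-arm comparison (normal approximation for two proportions): Φ(difference/SE − 1.96). The least favourable case with *s* = 25% is *p* = 15%, giving observed rates of 8.33% and 3.75%:

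- SE = √[(0.0833 × 0.9167 + 0.0375 × 0.9625)/1450] = 0.0088
- 0.0458/0.0088 = 5.20, and Φ(5.20 − 1.96) = 0.999

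So power stays above 99.9% for any share of 25% or more with placebo rates of 5% to 15%. At a share of 10% it runs from about 90% (*p* = 15%) to 99.99% (*p* = 5%). The loss falls on the estimates, not on the test.

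**The case against.** Several points on the other side have force.

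- **The open-ended sentence may not apply here.** Section 8.1 introduces the adverse event questions as additional to the pre-specified outcomes, and Section 12.2 says the eCRF does not yet exist. Directed questions on the Section 7.4 list are compatible with the text. This stands, so a reader should not infer that participants must volunteer the symptoms. The delay remains either way: a directed question at Tel 1 is still asked about 6 months after the infusion.
- **The infusion is a memory anchor.** Section 13.6 declines to analyse falls as time-to-event because "participants may not remember exactly when they fell", but falls occur on arbitrary days. Here the symptom follows a dated clinic visit, and participants are told beforehand what to expect, which may help recall as well as discourage calls. The parallel with falls is therefore only partial, and under-counting is a safer inference than wrong dating.
- **Comparisons may survive.** Both infusions have the same nominal delay, so an equal reporting share would leave the ratio of first to second infusion roughly intact. Section 13.7 plans no test between infusions and speaks of events reported, not prospectively captured.
- **The reaction is known, in a phase IV trial of a long-approved drug, and is not among the objectives in Section 3.** That limits the priority of the point but does not remove it, since the protocol chose to pre-specify and tabulate this outcome.

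**Conclusion.** The schedule and the planned analysis do not fit each other. Followed as written, the frequency of the first-listed safety outcome rests on recall over about 183 days or on unsolicited reports. The rate, the risk difference and the 3-day classification are likely to be under-estimated or imprecise.

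The delay follows directly from Table 1. The amount of under-reporting does not follow from anything in the protocol: the 25%, 17% and 8% figures illustrate assumed reporting shares and are not predictions.

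Three stronger readings are not supported:

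- That the symptoms last no more than 3 days. Sections 2, 6 and 13.7 say when they occur and give no maximum duration.
- That under-counting and mis-dating are certain. Both are inferences about recall.
- That a treatment difference would be missed. With equal reporting in both arms, power stays above 99.9% unless fewer than a quarter of cases are reported.

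This is an inexpensive improvement to make before data collection, not a threat to the trial's main conclusions.

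**What to change.** 1. State in Section 8.1 and Table 1 that the five post-infusion symptoms in Section 7.4 are asked as directed yes/no items, each with an onset date, at Tel 1 and Tel 4 and before the open-ended question.
2. At each infusion, hand out a one-page symptom card for the participant to complete over the first days and read out at the next scheduled call.
3. In Section 13.7, base the 3-day tables on the card, use the directed answers where the card is missing, and report by arm how many participants come from each source.

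Cost: no new visit, call or staff post. There are up to 2 × 2900 = 5800 cards to hand out and enter, and more non-serious events to record. Some cards will not be returned, so the tables gain a missing-data item. Prompting may raise reported rates slightly in both arms. Treatment and the primary analysis are unaffected.

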8.2. Serious adverse events

As recommended by the ICH,⁵⁰ an adverse event will be classified as a *serious adverse event* if it

- *results in death,*
- *is life-threatening,*
- *requires inpatient hospitalization or prolongation of existing hospitalization, or*
- *results in persistent or significant disability or incapacity.*

As also stated by the ICH,⁵⁰

Study Name: The Fragility Fracture Trial
Version No: 2
Date: 2020-10-04
EudraCT No: 2019-004766-17

Medical and scientific judgement should be exercised in deciding whether expedited reporting is appropriate in other situations, such as important medical events that may not be immediately life-threatening or result in death or hospitalisation but may jeopardise the patient or may require intervention to prevent one of the other outcomes listed in the definition above. These should also usually be considered serious.

8.3. Adverse drug reactions

An adverse event will be considered an *adverse drug reaction* (i.e., a causal link is suspected) if either the sponsor or the investigator considers there to be a reasonable possibility, based on evidence or arguments, that the event is causally related to an investigational product (zoledronic acid or placebo).⁵⁰ This definition of adverse drug reaction excludes adverse reactions to non-investigational products, such as vitamin D or other concomitant medications. If an adverse drug reaction meets the criteria for seriousness, it will be classified as a *serious adverse drug reaction*.⁵⁰

8.4. Unexpected and serious unexpected adverse reactions

An adverse reaction will be classified as an *unexpected adverse reaction* if its nature or severity is inconsistent with the Summary of Product Characteristics of Aclasta.^{17,51} If the unexpected adverse reaction is serious, it will be classified as a *suspected unexpected serious adverse reaction* (SUSAR).⁵¹

In accordance with EU guidelines (Paragraph 29),⁵² investigators must report serious adverse events to the sponsor within 24 hours of becoming aware of them. If the adverse event is a SUSAR, the sponsor will report it to the Swedish Medical Products Agency and to the Swedish Ethical Review Authority.⁵¹ SUSARs that are fatal or life-threatening will be reported within 7 days, and relevant follow-up information will be reported within an additional 8 days. Other SUSARs will be reported within 15 days. The sponsor will inform all principal investigators of SUSARs that occur.

With the help of the University Hospital of Umeå Clinical Research Centre, the sponsor will submit to the Swedish Medical Products Agency an annual Development Safety Update Report (DSUR), listing all serious adverse events and evaluating participant safety, as required by regulations (8 kap. 10 §).⁵³ The DSURs will comply with the ICH E2F guidelines.⁵⁴

Study Name: The Fragility Fracture Trial
Version No: 2
Date: 2020-10-04
EudraCT No: 2019-004766-17

9. Participant Timeline

A participant timeline can be found in Table 1. As shown, potential participants will be invited to a screening visit to provide written informed consent, to be assessed for eligibility, to be assigned a participant identification (ID) code, to undergo baseline testing, and to receive vitamin D. Of these steps, informed consent must come first, followed by assignment of a participant ID code. The baseline tests will include a self-administered health questionnaires (see the variables in Section 13.2) and measurements of body height and body weight (using a stadiometer and a medical scale). In addition, baseline tests of hand-grip strength will be conducted using hand dynamometers. Data on participants' baseline level of physical activity will be collected using hip-worn accelerometers. Participants will be asked to carry such an accelerometer on their non-dominant hip for 7 days. The device should be removed only at night and during showering, bathing, and swimming. The device should be set to record at 30 Hertz with 60 second epoch lengths. At the screening visit, all participants will receive a loading dose of oral vitamin D and a prescription for monthly oral vitamin D (see Section 6).

One week after the screening visit, participants will return for a randomization visit. At this time, participants will also return their accelerometer. The randomization visit may be cancelled by telephone if the results of the blood tests indicate that the participant does not meet the eligibility criteria. In this case, the patient will be informed that his or her participation ends here. If, on the other hand, the participant is still eligible, he or she will be infused with the next available bottle of investigational product. The next available bottle will be determined based on the sequential medication number with which each bottle is labeled. These bottles must be assigned to participants in the order in which they are labeled. The act of selecting a bottle is considered to be the act of randomizing the participant.

Follow-up interviews will be conducted by telephone every six months for 48 months for assessment of outcomes, adverse events, use of the prescribed vitamin D, and use of non-investigational bone-protective therapy. At every second interview, participants will be asked to complete the EQ-5D-5L online. The telephone interviews may be conducted with a next of kin if the participant is unable to respond and if the participant has consented to this. Halfway through the trial, at 24 months, participants will visit their study center for an in-person interview, outcome assessment, and a second infusion of zoledronic acid or placebo. Participants who have not taken their monthly vitamin D, or who have not taken a sufficient amount in the investigator's opinion, will receive a second loading dose of vitamin D one week before the second infusion. The final study contact, at 48 months, will be a telephone interview instead of an in-person visit to reduce the burden on investigators. Participants will be followed through registers for ten years after randomization, so that the long-term effects of zoledronic acid can be evaluated. Participants will be given the choice to opt out of registry follow-up.

Study Name: The Fragility Fracture Trial
Version No: 2
Date: 2020-10-04
EudraCT No: 2019-004766-17

Investigators must do their best to ensure that study contacts occur in the designated time windows by scheduling study contacts in good time. To reduce the burden on investigators, telephone interviews will be conducted centrally from the sponsor/coordinating investigator's center. Each visit is anticipated to take 1 hour and each telephone interview 30 minutes.

Study Name: The Fragility Fracture Trial
Version No: 2
Date: 2020-10-04
EudraCT No: 2019-004766-17

Table 1. Participant Timeline

Timing/procedure	Event										
	Scr	Rand	Tel 1	Tel 2	Tel 3	Vis 1	Vis 2	Tel 4	Tel 5	Tel 6	Tel 7
Time point	-7 d	0	6 m	12 m	18 m	23 m + 3 w	24 m	30 m	36 m	42 m	48 m
Time window	-4 to -1 w	0	±4 w	±4 w	±4 w	±4 w	±4 w	±4 w	±4 w	±4 w	±4 w
Informed consent	X										
Eligibility	X	X*				X**	X*				
Participant ID code	X										
Health questionnaire	X										
Body weight	X										
Blood samples	X					X					
Accelerometer	X										
Vitamin D loading dose	X					X [†]					
Vitamin D prescription	X		X	X	X	X		X	X	X	
Infusion		X					X				
Oral vitamin D use			X	X	X	X		X	X	X	X
Bone-protective drug use			X	X	X	X		X	X	X	X
Adverse event assessment			X	X	X	X		X	X	X	X
Outcome assessment			X	X	X	X		X	X	X	X
Fractures			X	X	X	X		X	X	X	X
Death			X	X	X	X		X	X	X	X
MIMI			X	X	X	X		X	X	X	X
Stroke			X	X	X	X		X	X	X	X
Falls			X	X	X	X		X	X	X	X
Cancer			X	X	X	X		X	X	X	X
Body height	X					X					
Hand-grip strength	X					X					
EQ-5D-5L	X			X		X			X		X

Abbreviations: D, day; EQ-5D-5L, EuroQol-5 Dimensions-5 Levels; M, month; MI, myocardial infarction; Rand, randomization; Scr, Screening; Tel, telephone interview; Vis, visit to study center for follow-up; W, week

*Assessment of laboratory values

** Assessment of qualification for second infusion

[†] A second loading dose of vitamin D should only be given if the participant has not taken the prescribed monthly vitamin D (or a sufficient amount, in the investigator's opinion)

Study Name: The Fragility Fracture Trial
Version No: 2
Date: 2020-10-04
EudraCT No: 2019-004766-17

10. Treatment Allocation and Blinding

Participants will be randomized according to a 1:1 permuted-block design, with randomly varying block sizes. Randomization will not be stratified by study center, so that the investigational products can be distributed from a central location to any study center as needed. To guarantee balance in group sizes within centers, the investigational products will be delivered in boxes containing multiple complete blocks. Centers will obtain investigational products by placing a request to the sponsor, who must authorize delivery from the central location. As zoledronic acid has a limited shelf life, the first and second rounds of treatment will be produced, labeled, and delivered separately.

The trial statistician will use a computerized random number generator to create a randomization list, which will contain a sequential medication number (0001, 0002, etc.) and the corresponding treatment assignment (zoledronic acid or placebo). The randomization list will be sent to the manufacturer of the investigational products, who will label each bottle with a medication number and fill it with the appropriate content. Apart from these numbers, the bottles will be visually identical in terms of content, packaging, labeling, and delivery. If possible, the manufacturer will attach a tear-off label to each bottle, which can be torn off to determine the content of the bottle if emergency unblinding is needed. If this is not possible, each box of investigational products will instead contain sealed envelopes with information about the content of each bottle. These envelopes will only be opened in the case of emergency unblinding, when knowledge of the assigned treatment is necessary to protect participants' health. Investigators will be responsible for registering instances of intentional and unintentional unblinding on electronic case report forms (eCRFs).

As mentioned, the randomization list will be generated using a computer program written by the trial statistician. However, to maintain the trial statistician's blinding, this program will be run by staff at the University Hospital of Umeå Clinical Research Centre. The Research Centre will also be responsible for sending the randomization list to the manufacturer of the investigational products. The randomization list will then be stored by the Research Centre in a locked and safe location. Access to the randomization list will be granted to independent monitors and inspectors upon request, but not to anyone directly involved in the study.

It will not be possible for clinical personnel to predict treatment assignment, because the randomization list will be stored securely and the investigational products will be visually identical apart from the above-mentioned sequential medication numbers. The trial statistician will not reveal the block sizes to anyone else directly involved in the trial (e.g., the sponsor, principal investigators, or investigators' staff).

The study will be double blind. Therefore, the participants, the sponsor/coordinating investigator, the trial statistician, the principal investigators, and the principal investigators' staff will be unaware of the participants' treatment assignment. Participants will be informed of their treatment assignment when they have completed 48 months of follow-up or when

Study Name: The Fragility Fracture Trial
Version No: 2
Date: 2020-10-04
EudraCT No: 2019-004766-17

they withdraw from the study. This information will be provided by a research nurse or a member of the administrative staff. The research nurses and administrative staff will obtain information on treatment assignment using the method of emergency unblinding described above (i.e., not by accessing the entire randomization list). They will not spread this information to other staff members, including the principal investigators, the sponsor/coordinating investigator, or the trial statistician. Treatment assignments will be unblinded to other staff at the end of the trial, when the randomization list is unlocked. This list will be unlocked when the sponsor/coordinating investigator and the trial statistician have confirmed that the trial database is accurate and complete and when an analysis dataset has been compiled.

11. Recruitment

Potentially eligible patients will be identified through searching the Swedish Fracture Register for persons who have recently sustained a fracture. The Swedish Fracture Register was established in 2011 to monitor fracture occurrence, fracture care, and health outcomes after a fracture.⁵⁵ All patients in this register have agreed to the use of their information in research, although they have not signed consent forms, as this is not required by Swedish law.⁵⁵ When potentially eligible patients have been identified through the Fracture Register, they will be contacted through postal mail, followed by a telephone call to ask whether they are interested in participating.

Recruitment through the Swedish Fracture Register has two advantages. First, we consider it to be more respectful than approaching patients in emergency rooms, where they are in pain and in need of medical attention. Second, it will make it easier to recruit the necessary number of participants. If the Swedish Fracture Register has insufficient coverage of fracture patients at a participating hospital, potentially eligible subjects may instead be identified through local patient records (e.g., emergency ward or X-ray records) or fracture liaison services (*Swedish*: “*frakturkedjor*”).

12. Data Collection

